A Pearson's Chi Squared test for independence will be used to test the hypotheses states in Section 4.7.1 that there is no difference between the combined treatment and each individual component at Visits 3 and 4. If less than 80% of the expected counts are less than 5 or at least one category has no patients in a treatment group, then Fisher's exact test will be used. Differences in response rates with the corresponding 95% CIs will be reported. Sensitivity analyses to investigate the impact of the choice of method for handling missing data and the choice of analysis population will be performed as described in Section 4.7.1.3.

The homogeneity of the treatment effect for a number of important subgroups will be investigated as described in Section 4.7.1.4.

A by-patient listing of the therapeutic response will be provided.

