If a patient took rescue medication prior to Visit 3, the response will be considered not resolved at Visit 3. Similarly, if a patient took rescue medication prior to Visit 4, the response will be considered not resolved at Visit 4.

For Visits 3 and 4, the proportion of patients with a response of Resolved and Not Resolved will be compared between the treatment groups by using the same Chi-squared test as the primary efficacy endpoint.

A by-patient listing of edema data will be provided.

Otorrhea

Otorrhea will be assessed by the Investigator at Visits 1, 3 and 4. Otorrhea will be assessed as Severe, Moderate, Mild, or Absent as defined in Section 4.7.2.

The number and percentage of patients with each outcome (Severe, Moderate, Mild or Absent) will be summarized by visit and treatment group.

Assessments will also be summarized in terms of a 3-level and a 2-level response. For the 3-level response, otorrhea will be considered resolved at Visits 3 and 4 if the otorrhea is assessed as Absent. Otorrhea will be considered as "Improved" at Visit 3 and Visit 4 if otorrhea is assessed by the investigator as "Mild" and was assessed as "Severe" or "Moderate" at Visit 1 (Day 1) or if otorrhea was assessed by the investigator as "Moderate" at Visit 3 or Visit 4 and was assessed as "Severe" at Visit 1. Otorrhea will be considered as "Not Improved" otherwise. Furthermore if otorrhea is considered "Not Improved" or "Improved" in the 3-level response then it will be identified as "Not Resolved" in the 2-level response. If otorrhea is considered "Resolved" in the 3-level response then it will also be considered "Resolved" in the 2-level response.

If a patient took rescue medication prior to Visit 3, the response will be considered not resolved at Visit 3. Similarly, if a patient took rescue medication prior to Visit 4, the response will be considered not resolved at Visit 4.

For Visits 3 and 4, the proportion of patients with a response of Resolved and Not Resolved will be compared between the treatment groups by using the same Chi-squared test as the primary efficacy endpoint.

A by-patient listing of otorrhea data will be provided.

Ear Pain Scales

Ear pain scales will be assessed by the patient twice a day in the patient's Diary Card to calculate the TEOP. The ear pain scales assessed at Visit 3 and Visit 4 will be categorized as follows:

- Disappeared if there is no ear pain
- Improved if the response is better than the response at Visit 1

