- No change if the response is the same as the response at Visit 1
- Worsened if the response is worse than the response at Visit 1
- Missing if there is no response

The number and percentage of patients with each outcome will be summarized by visit and treatment group for each pain scale and for all pain scaled combined. The proportion of patients with the responses will be compared between the treatment groups by using the same Chi-squared test as the primary efficacy endpoint.

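### The Ear Pain Scales analysis compares ordered response categories with an unordered chi-squared test; the loss of power can only be illustrated, and the categories tested and the place of Missing need stating

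*SAP*

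**What the plan says.** SAP 4.7.3, Ear Pain Scales, defines five categories for the diary scales at Visits 3 and 4. Disappeared means that no pain is left. The next is defined as "Improved if the response is better than the response at Visit 1"; No change and Worsened are judged against the same Visit 1 value. The fifth has no place in this order: "Missing if there is no response".

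Counts and percentages are tabulated by visit and arm, for each pain scale and for all scales together. The test is then given in one sentence: "The proportion of patients with the responses will be compared between the treatment groups by using the same Chi-squared test". The sentence goes on to refer to the primary endpoint, and SAP 4.7.2 identifies the test used there. A Pearson "Chi Squared test for independence will be used to test the hypotheses" of the combination against each component, with Fisher's exact test as fallback.

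The neighbouring analyses are handled differently. In SAP 4.7.3, overall clinical outcome is collapsed to two groups before testing, and Brighton grading, otalgia, edema and otorrhea are each reduced to Resolved or Not Resolved. Ear Pain Scales has no such step.

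**The concern.** The primary outcome has two categories, cure and failure, and a Pearson test suits it. Applied to four ordered categories, the same test has 3 degrees of freedom and takes no account of order: exchanging the labels Disappeared and Worsened leaves the p-value unchanged. Two things follow.

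- A benefit that moves patients toward less pain is spread over three degrees of freedom and is easier to miss.
- A significant result need not mean that the combination is better. It could arise from a difference between No change and Worsened alone.

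Apart from time to end of ear pain (TEOP), this is the only planned between-arm test of pain as recorded in the diary; otalgia is rated by the investigator.

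**Working it through.** **1. The plan's own figure.** The sample size section (SAP 4.10) gives 150 per large arm for therapeutic cure: 62% against a relative 25% increase, two-sided 5%, 80% power. With 0.62 × 1.25 = 0.775, the two-proportion formula gives 136.7 per arm. The continuity correction, (n/4)·[1 + √(1 + 4/(n × 0.155))]², gives 149.3, so 150. The plan's figure reproduces. It is for the primary endpoint; no power or category distribution is given for Ear Pain Scales.

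**2. Inputs for an illustration.**

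- From the documents: 150 per arm, two-sided 5%, and the rates 62% and 78%.
- Assumed: that these cure rates stand in for the proportion Disappeared; proportional odds, with OR = (0.78/0.22)/(0.62/0.38) = 2.17; and three splits of the remaining 38% in the ciprofloxacin arm over Improved / No change / Worsened (28/6/4, 23/10/5, 33/3/2).

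**3. Formulas.** Let m_j be the pooled proportion in category j.

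- Pearson: λ = Σ_arms n Σ_j (p_j − m_j)²/m_j, on 3 df.
- Score test: λ = d²/[v(1/n₁ + 1/n₂)], on 1 df, where d is the difference in mean score and v the pooled score variance.
- Power is the probability that a non-central chi-squared variable with that λ exceeds the 5% critical value.

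**4. One split in full.** Ciprofloxacin 62/23/10/5% and OR 2.17 give 78.0/14.5/5.1/2.4% for the combination.

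- Pearson: λ = 300 × (0.00914 + 0.00966 + 0.00776 + 0.00474) = 9.39; power on 3 df 73.1%.
- Ridit scores: d = 0.0823, v = 0.0542, so λ = 0.00678/(0.0542 × 2/150), about 9.39; power on 1 df 86.5%.
- Integer scores: power 82.0%.
- Disappeared against the rest: λ = 0.16²/(0.7 × 0.3 × 2/150) = 9.14; power 85.6%.

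The ridit test captures the same λ on one degree of freedom that the Pearson test spreads over three.

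**5. All three splits, 150:150.**

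| Test | Power |
|---|---|
| Pearson, 3 df | 72.4-73.1% |
| Ridit scores, 1 df | 86.0-86.5% |
| Integer scores, 1 df | 80.7-82.0% |
| Disappeared vs rest, 1 df | 85.6% |

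The loss is 13-14 points against ridit scores and 8-9 against integer scores. A simulation with a fourth split (62/25/9/4) gave Pearson 73.0%, Wilcoxon 86.9% and equally spaced scores 82.7%.

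**6. Other assumptions.**

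- Five splits, each with the effect set to give about 80% Wilcoxon power: the loss against Wilcoxon is about 16-17 points at 150:150 and 12-14 at 150:75; against equally spaced scores, about 10-13 and 5-11.
- Fluocinolone (75 patients) with an assumed 40-50% Disappeared against 78%: Pearson 97-99.9%, ridit 99-100%, a loss of about 0-2 points.
- A pattern that is not a shift (72/13/10/5 against 62/25/9/4): Pearson 60%, Wilcoxon 30%, equally spaced scores 11%. Here the unordered test wins.
- Missing tested as a fifth category, 10-20% in both arms: Pearson 63.0% and 56.8%, against Wilcoxon among responders 83.3% and 78.9%.

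**The case against.** **The sentence may mean a two-level test.** The primary comparison is two-by-two, and so are the sign and symptom analyses that borrow it. If Disappeared against the rest was intended, power is 85.6% and the loss against ridit scores is under 1 point. This stands as a possible reading, but the SAP does not say so. The plural reference to responses, and the explicit collapsing everywhere nearby, point the other way. On either reading the sentence needs completing.

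**The size is not in the documents.** A reader might infer that the plan gives up about 13 points of power. The documents do not support that as a fact: 62% and 78% are therapeutic cure rates, which also require absent edema and otorrhea and bacterial eradication, and the rest of the distribution is assumed.

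**Direction is not lost.** A reader might infer that the report could not show which arm did better. Percentages by arm are tabulated, so it can; only the p-value lacks direction.

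**Pearson may not be the test run.** SAP 4.7.2 switches to Fisher's exact test under its expected-count rule or when a category is empty in an arm. Taken literally, the rule sent every simulated table to Fisher. This stands as a limit on the Pearson figures, but Fisher's test is unordered too.

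**The test is within the protocol, and the stakes are low.** The protocol synopsis allows chi-squared or Cochran-Mantel-Haenszel, as appropriate, for other secondary endpoints. Protocol 10.1.10.2 makes those analyses supportive only, and Ear Pain Scales is not listed among the endpoints in SAP Section 2. Both points stand.

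**Conclusion.** The point holds as a minor improvement. As written, ordered categories go to an unordered omnibus test whose p-value neither uses the order nor shows which arm did better.

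Under proportional odds, 62% against 78% Disappeared and 150 per arm, the cost is roughly 8-14 points of power, depending on the scores used, and up to about 17 under other assumed splits and effects. It is close to nil if the effect against fluocinolone is large or a two-level test was meant, and it reverses if the effect is not a shift.

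A reader might take this as a threat to the trial's main claims. It is not: neither the primary analysis nor TEOP uses this test.

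**What to change.** In SAP 4.7.3, Ear Pain Scales, replace the sentence on the test with:

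> The ordered categories Disappeared, Improved, No change, Worsened will be compared between the combination and each component by the Cochran-Mantel-Haenszel row-mean-scores test with modified ridit scores, stratified by pain scale for the all-scales-combined comparison. Patients with Missing will be placed in the worst category, consistent with Section 4.7.1.1, with a sensitivity analysis excluding them.

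Keep the planned counts and percentages. Missing has to be named because it has no place in the order, and SAP 4.7.1.1 counts missing efficacy data as failure; an ordinal test that listed only four categories would drop those patients silently. Stratifying by pain scale fits the plan to pool three instruments. It differs from the two-level age factor used for TEOP, and the SAP should say so.

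If a two-level test was intended, state Disappeared versus all others instead. That recovers nearly all the power in the illustration and gives a direction.

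The cost is one sentence before database lock and a standard option of a method already used in SAP 4.7.1.4, with no new data or patients. The drawback is less sensitivity to differences that are not a shift toward better or worse.

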4.8 Safety Evaluation

All safety analyses will be based on the Safety population as defined in Section 4.4.

4.8.1 Extent of Exposure

Exposure as measured by duration of treatment will be summarized by treatment group. Extent of exposure will be calculated for the treatment period.

Days of exposure will be calculated for each patient: (date of last dose of treatment drug – date of first dose + 1).

The duration of study participation will be calculated as (the latest of (last visit/follow-up date or study termination date) – randomization date + 1.

Exposure data will be listed.

4.8.2 Adverse Events

Adverse events will be coded using the MedDRA Version 20.0. Adverse events will be tabulated by body system, preferred term, and treatment group.

Treatment-emergent adverse events (TEAEs) will be tabulated for the following subsets:

1. All TEAEs;
2. Related TEAEs;
3. Serious adverse events (SAEs);
4. Related Serious TEAEs;
5. Adverse events leading to study discontinuation;
6. Adverse events leading to discontinuation of study medication;
7. Adverse events resulting in death;

Tabulations of AEs by body system, preferred term, treatment group, and severity, and by body system, preferred term, treatment group, and relationship to study medication will also be provided.

The data will be displayed as number of subjects experiencing the AE, percentage of subjects, and number of AEs. All AE summaries will provide the number of patients reporting at least 1 AE and the total number of events reported.

General Rules for Adverse Events

1. An AE will be considered as treatment-emergent if it begins on or after the first study drug dosing or that worsens in severity after at least 1 dose of study drug has been administered. In case of insufficient information to determine if the event occurred before, during or after study drug dosing, the AE will be considered as treatment-emergent.

The imputation method for the handling of missing or partial dates will be as follows:

Start dates

- If the day is missing, but month and year are present and the same as the month and year of the first dose of study drug, then day will be set to the same day as the start of study drug. Otherwise, this will be imputed as the first day of the month.
- If the month is missing, but year is present and the same as the year of the first dose of study drug, then month will be set to the same month as the start of study drug. Otherwise, this will be imputed as January.
- If the year is missing, the event will be considered as treatment emergent and the start date will be imputed as the date of first treatment.

Stop dates

- If the day is missing, this will be imputed as the last day of the month, or the last day of participation in the study if the AE end month is the same as the last date of participation in the study.
- If the month is missing, this will be imputed as December, or the last month of participation in the study if the AE end year is the same as the last date of participation in the study
- If the year is missing, the AE will be considered as ongoing and no imputation of the date will occur.

2. Patients will be classified as having withdrawn from the study due to an AE if the patient had a study drug action taken recorded as "permanently discontinued" on the Adverse Events page of the eCRF or patient had the study completion item recorded as 'No' with 'Adverse Event' as the primary reason for discontinuation on the study completion page of the eCRF.

3. AEs that occur before the first dose of study treatment will not be reported/summarized but will be listed as non-TEAE.
4. If a patient experiences more than one AE in a particular SOC, they will only be included once in the count for the SOC but will appear in the count for each appropriate PT within the SOC (unless it is the same PT).
5. AEs related to study drug tables will include only those AEs with a relationship to study drug of 'related', 'probable', 'possible', or if there is a missing relationship on the AE page of the eCRF.
6. For AE causality, when there is more than one AE of the same PT, the most related will be considered in the summary tables by causality.
7. For AE severity, when there is more than one AE of the same PT, the worst severity will be considered in the summary tables by severity.
8. If severity is missing, the event will be considered serious.

The AEs will be ordered by decreasing frequency, then alphabetically, for total patients for each SOC and PT within an SOC.

TEAEs will also be summarized by age group.

An overall summary of AEs will be provided by treatment group and overall. The summary will include incidences for the following:

- Any TEAE
- Any Treatment Related TEAE
- Any SAE
- Any Treatment Related SAE
- Any TEAE leading to Study Discontinuation
- Any TEAE leading to Permanent Study Medication Discontinuation
- Any TEAE resulting in death
- Severe TEAE
- Severe related TEAE

A by-patient listing of all adverse events (including non-treatment-emergent events) will be provided. This listing will be presented by treatment group and will include: center, patient identifier, age, sex, race, AE (SOC, PT, and verbatim term), date of onset, date of resolution, duration, severity, seriousness, seriousness criteria, action taken, outcome and causality.

Patients reporting the same AE more than once will be counted only once for this event in the AE summary table. For tabulation by severity, the AE with the greatest severity reported by the patient will be included in the table. Similarly, for tabulation by relationship to study medication, the AE with the closest relationship to study medication will be included in the table.

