### **5.3 Withdrawal, Premature Discontinuation of Study Medication, and Replacement of Patients**

Patients must be withdrawn from the study if they withdraw consent to participate. Such withdrawal may occur at any time during the study. Patients are not required to state their reasons for withdrawing consent.

Patients who do not experience improvement in symptoms may prematurely discontinue treatment with study medication. This protocol includes an assessment of whether a patient who experiences no improvement at Visit 2 should discontinue study treatment, as described in Section 8.2.2. However, a patient may discontinue study treatment at the Investigator's discretion at any time during the study treatment period.

Patients may be required to discontinue study treatment after discussion with the Sponsor and/or Investigator for any of the following reasons:

- Adverse event(s);
- At the discretion of the Investigator;
- Violation of eligibility criteria; or
- Deviation from the treatment plan specified in the protocol (e.g., incorrect administration of study medication, failure to attend study visits).

In all cases, the reasons for premature discontinuation of study medication must be recorded in the Electronic Data Capture (EDC) and in the patient's medical records. If there is more than one reason for premature discontinuation of study medication, one reason will be listed in the EDC as the primary reason.

If possible, each patient who prematurely discontinues study treatment should report to the study site for an End of Treatment visit (Visit 3), as described in Section 8.2.3.

Patients who withdraw consent or discontinue study medication prematurely will not be replaced.

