4.3 Study Patients

4.3.1 Disposition of Patients

Information on the disposition of all patients who enter the study will be provided, from screening to study completion.

The following patient data will be presented by treatment group, including overall categories:

- The number of patients screened (overall only)
- The number of patients who were screen failures (overall only)
- The number of patients randomized
- The number of patients randomized with pathogen positive culture
- The number of patients randomized with positive culture for *P. aeruginosa* and/or *S. aureus*
- The number and percent of patients who were treated/not treated
- The number of patients in the Clinical Per-Protocol (CPP) population
- The number of patients in the Microbiological Per-Protocol (MPP) population
- The number and percent who completed the study
- The number and percent of patients who withdrew from study drug

Percentages of patients will be based on the number of patients randomized as 100%. The number and percentage of patients who withdrew (early terminated) during the study will be presented by reason for study discontinuation. The number and percentage of patients who withdrew from study medication will be presented by reason for study medication discontinuation.

In addition, patient listings will be provided for patients who discontinued the study early (post-randomization) with reason for discontinuation. Screen failed patients will also be listed with reason for screen failure.

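### SAP 4.8.2 item 2 treats a permanent stop of study drug for an AE as withdrawal from the study, so the AE study-discontinuation count may include patients still in follow-up

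*SAP*

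**What the plan says.** Item 2 of the general rules in SAP 4.8.2 has two limbs. The first reads "Patients will be classified as having withdrawn from the study due to an AE if the patient had a study drug action taken recorded"; the entry it requires is a permanent stop, taken from the AE page of the eCRF. The second reads "or patient had the study completion item recorded as 'No' with 'Adverse Event' as the primary reason for discontinuation on the study completion page". They are joined by *or*, so either is sufficient.

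The same section lists two separate tabulations, "Adverse events leading to study discontinuation" and "Adverse events leading to discontinuation of study medication". The overall AE summary repeats the split in two rows, "Any TEAE leading to Study Discontinuation" and "Any TEAE leading to Permanent Study Medication Discontinuation". Protocol 10.1.11 also names discontinuation from the study and from the study medication as two things.

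Disposition keeps them apart too. SAP 4.3.1 presents early termination from the study by reason for study discontinuation, and adds: "The number and percentage of patients who withdrew from study medication will be presented by reason for study medication discontinuation".

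On conduct, Protocol 5.3 states "Patients may be required to discontinue study treatment after discussion with the Sponsor and/or Investigator for any of the following reasons", and adverse events head that list. It asks anyone who stops treatment early to attend Visit 3 if possible. Protocol 8.2.4 excuses from Visit 4 only patients who were withdrawn from the study or who withdrew consent.

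**The concern.** Stopping the drug and leaving the study are different events in this trial, and the plan orders separate outputs for each. The first limb of item 2 merges them: a patient who stops drops because of an AE and then attends every later visit would be labelled as withdrawn from the study due to an AE.

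What is at stake is a safety count in the study report of a trial meant to support a US marketing application (Protocol 2.2). The number of AE-related study withdrawals could be too high and could disagree with the disposition table in the same report. The patients who came off drug but were still followed, whom separate outputs would reveal, would no longer be visible from the two AE tables.

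**Working it through.** The documents state no figure on this point, so there is nothing to reproduce. The check is one of set logic.

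**Does the protocol allow a drug stop without study withdrawal?** Protocol 5.3 lists AEs as a reason to stop treatment and requests Visit 3 afterwards. Protocol 8.2.4 does not list stopping drug among the exemptions from Visit 4. The protocol expressly ties stopping drug to withdrawal from the study in one situation only: non-improvement after the Visit 2 call, option 2 (Protocol 4.1 and 8.2.2). That is not a rule for AEs. So the combination is foreseen.

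**Groups.** Let

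- n11 = drug permanently stopped for an AE, and study completion recorded as No with AE as primary reason;
- n10 = drug permanently stopped for an AE, but not recorded as leaving the study for an AE (completed follow-up, or left for another primary reason);
- n01 = recorded as leaving the study for an AE, with no permanently discontinued action on the AE page (for example, after finishing the 7 days of dosing).

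**Counts of patients.**

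- Study medication discontinuation due to AE: D = n11 + n10.
- Study discontinuation due to AE under item 2: U = n11 + n10 + n01.
- Disposition, study discontinuation with AE as reason: S = n11 + n01, assuming this reason is taken from the completion page.

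**Differences.** U − D = n01, which is never negative. U − S = n10. With item 2 split by source, the study-discontinuation count becomes n11 + n01 = S, and D is unchanged.

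The counts below are hypothetical and only show how the rule behaves:

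| n11, n10, n01 | D (drug) | U (study, item 2) | S (disposition) | Excess U − S | Study count after split |
|---|---|---|---|---|---|
| 5, 0, 0 | 5 | 5 | 5 | 0 | 5 |
| 3, 2, 0 | 5 | 5 | 3 | 2 | 3 |
| 0, 5, 0 | 5 | 5 | 0 | 5 | 0 |
| 3, 2, 1 | 5 | 6 | 4 | 2 | 4 |
| 5, 0, 1 | 5 | 6 | 6 | 0 | 6 |

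The excess is always n10, whatever the other two groups are.

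**Likely scale.** The plan gives no expected number of AE-related stops. Protocol 2.3 reports, for the sponsor's earlier AOE trial of 590 subjects, 7 subjects with non-serious AEs and 1 with an SAE. If that rate carried over to 500 patients (an assumption, since dosing and presentation differed), any AE at all would be expected in about 500 × 7/590 = 5.9 to 500 × 8/590 = 6.8 patients. The n10 group is a subset of these, so zero or very few is plausible.

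**The case against.** The strongest reply is that item 2 may not drive the tables at issue. It classifies patients, whereas the tabulations select events. SAP 4.8.3 also plans an overview of patients who discontinued due to AEs without separating drug from study, and an either-source rule would suit that output. SAP 4.2 leaves programming details to the mock shells, which are not available here, and nor is the eCRF. This stands as a limit on certainty. It does not remove the point: item 2 speaks of withdrawal from the study, which fits a pooled overview poorly, and the SAP offers no other definition for a programmer to apply to the study-discontinuation table and row.

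The follow-up premise is partly inferred. No sentence says outright that a patient who stops drug for an AE goes on to Visit 4; this follows from the exemptions in Protocol 8.2.4. The Visit 3 request in 5.3 is qualified by feasibility, and the schedule of observations speaks of early termination where Protocol 8.2.3 speaks of early discontinuation of study treatment. The inference is still the natural one.

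SAP 4.3.1 names no eCRF field for the disposition reason, so the comparison with disposition rests on the assumption stated above. Other outputs would also let a reader trace any discrepancy: medication withdrawal by reason, action taken in the AE listing, and the listing of AEs leading to discontinuation.

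A reader might infer two stronger things. One is that the two AE tables must come out the same. They need not, because patients who leave for an AE without a permanent drug stop (n01) appear only in the study table. The other is that the AE table is bound to contradict disposition. It does so only if n10 is at least 1; the first and last rows of the table above show agreement.

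**Conclusion.** The point holds as a conditional error of definition. Read literally, item 2 makes a permanent drug stop for an AE sufficient for study withdrawal due to an AE, against the separation kept elsewhere in SAP 4.8.2, in SAP 4.3.1 and in Protocol 10.1.11. The study-discontinuation count is overstated by exactly the number of patients who stop drug for an AE but are not recorded as leaving the study for one.

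This rests on item 2 being applied to the study-discontinuation table and row; the mismatch with disposition rests further on disposition using the completion-page reason. The expected number is unknown and probably small. The effect is confined to safety reporting and its agreement with disposition. The efficacy definitions and missing-data rules do not use item 2, and neither the significance level nor the sample size is touched. This is a minor correction, worth making because it is nearly free.

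**What to change.** Split item 2 into two definitions before database lock:

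- *Withdrawn from the study due to an AE*: study completion recorded as No, with Adverse Event as the primary reason on the completion page.
- *Discontinued study medication due to an AE*: action taken recorded as permanently discontinued on the AE page.

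Use each for its own table and its own row in the overall summary, and confirm that the shells follow. State in SAP 4.3.1 that the study-discontinuation reason comes from the completion page, so that the two counts reconcile. If a pooled count is wanted for the overview in SAP 4.8.3, define it separately as either event and label it so. The cost is SAP wording and a check of the shells; both data fields are already named in item 2, so no new data and no change in conduct are needed.
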